14.1.36 Incomplete dates for last known date patient alive or death

All dates must be completed with day, month and year. If the day is missing, the 15th of the month will be used for incomplete death dates or dates of last contact.

14.1.37 Non-target lesion response

If no non-target lesions are identified at baseline (and therefore not followed throughout the study), the non-target lesion response at each assessment will be considered ‘not applicable (NA)’.

14.1.38 Study/project specific programming

The standard analysis programs need to be adapted for each study/project.

14.1.39 Censoring reason

In order to summarize the various reasons for censoring, the following categories will be calculated for each time to event variable based on the treatment completion page, the study evaluation completion page and the survival page.

For survival the following censoring reasons are possible:

[figure not shown]
- Alive
- Lost to follow-up

For PFS and TTP (and therefore duration of responses) the following censoring reasons are possible:

- Ongoing without event
- Lost to follow-up
- Withdrew consent
- Adequate assessment no longer available*
- Event documented after two or more missing tumor assessments (optional, see [Table 14-5](#))
- Death due to reason other than underlying cancer (*only used for TTP and duration of response*)
- Initiation of new anti-cancer therapy

*Adequate assessment is defined in [Section 14.1.25](#). This reason is applicable when adequate evaluations are missing for a specified period prior to data cut-off (or prior to any other censoring reason) corresponding to the unavailability of two or more planned tumor assessments prior to the cut-off date. The following clarifications concerning this reason should also be noted:

- This may be when there has been a definite decision to stop evaluation (e.g. reason “Sponsor decision” on study evaluation completion page), when patients are not followed for progression after treatment completion or when only UNK assessments are available just prior to data cut-off).
- The reason "Adequate assessment no longer available" also prevails in situations when another censoring reason (e.g. withdrawal of consent, loss to follow-up or alternative anti-cancer therapy) has occurred more than the specified period following the last adequate assessment.
- This reason will also be used to censor in case of no baseline assessment.

14.2 Appendix 2 - ECOG/WHO performance status scale

Table 14-6 ECOG performance status

[figure not shown]
Grade	ECOG status
0	Fully active, able to carry on all pre-disease performance without restriction
1	Restricted in physically strenuous activity but ambulatory and able to carry out work of a light or sedentary nature e.g., light house work, office work
2	Ambulatory and capable of all self-care but unable to carry out any work activities. Up and about more than 50% of waking hours
3	Capable of only limited self-care, confined to bed or chair more than 50% of waking hours
4	Completely disabled. Cannot carry on any self-care. Totally confined to bed or chair
5	Dead

[figure not shown]

[Redacted text block]

[Redacted text block]

[Redacted text block]

14.4 Appendix - 4 Prohibited concomitant medications

[figure not shown]
In general, the use of any concomitant medication deemed necessary for the care of the patient is permitted in this study, except as specifically prohibited below. Administration of study drug could result in drug-drug interactions (DDI) that could potentially lead to reduced activity or enhanced toxicity of the concomitant medication and/or LEE011.

The following lists are based on the Oncology Clinical Pharmacology Drug-Drug Interaction Database (release date: 29 Oct 2012), which was compiled from the Indiana University School of Medicine’s “Clinically Relevant” Table and supplemented with the FDA Draft Guidance for Industry, Drug Interaction Studies – Study Design, Data Analysis, and Implications for Dosing and Labeling (February 2012), and the University of Washington’s Drug Interaction Database. These lists are not comprehensive and are only meant to be used as a guide. Please contact the medical monitor with any questions.

14.4.1 Prohibited medications

Table 14-7 List of prohibited medications during LEE011 treatment

Category	Drug Name
Strong CYP3A Inhibitors	boceprevir, clarithromycin, conivaptan, grapefruit juice, indinavir, itraconazole, ketoconazole, lopinavir/ritonavir, mibefradil, nefazodone, nelfinavir, posaconazole, ritonavir, saquinavir, sequinavir/ritonavir, telaprevir, telithromycin, voriconazole, indinavir/ritonavir, tipranoavir/ritonavir, cobicistat, troleandomycin, danoprevir/ritonavir, eltegravir/ritonavir
Strong CYP3A Inducers	avasimibe, carbamazepine, phenytoin, rifampin, St. John’s wort ² , rifabutin, phenobarbital, mitotane, enzalutamide
CYP3A substrates with NT1 ¹	quinidine, astemizole, terfanadine, cyclosporine, sirolimus, tacrolimus, diergotamine, cisapride, ergotamine, pimoziide, alfentanil, fentanyl, thioridazine, diergotamine, dihydroergotamine, ergotamine
Medications that carry a strong risk for QT prolongation/TdP	amiodarone, anagrelide, arsenic trioxide, astemizole, azithromycin, bepridil, chloroquine, chlorpromazine, cisapride, citalopram, clarithromycin, cocaine, disopyramide, dofetilide, domperidone, dronedarone, droperidol, erythromycin, escitalopram, flecainide, grepafloxacin, halofantrine, haloperidol, ibutilide, levofloxacin, levomethadyl, mesoridazine, methadone, moxifloxacin, ondansetron, pentamidine, pimoziide, probucol, procainamide, quinidine, sevoflurane, sotalol, sparfloxacin, sulpiride, terfenadine, thioridazine, vandetanib
Other investigational and antineoplastic therapies	Other investigational anticancer therapies including chemotherapy, biologic or radiation therapy, and surgery must not be used while the patient is on the study. If such agents are required for a patient then the patient must be discontinued from the study.
Herbal medications	Herbal preparations/medications are prohibited throughout the study. These herbal medications include, but are not limited to: St. John’s wort, Kava, ephedra (ma huang), ginkgo biloba, dehydroepiandrosterone (DHEA), yohimbe, saw palmetto, and ginseng. Patients should stop using these herbal medications 7 days prior to first dose of study drug.
Hematopoietic growth factors	Hematopoietic growth factors (e.g. erythropoietins, G-colony stimulating factor (CSF) and GM-CSF) are not to be administered for primary prophylaxis. Use of these drugs should be reserved to patients with severe neutropenia and anemia as per the labeling of these agents or as dictated by local practice (see also the guidelines established by the American Society of Clinical Oncology (ASCO)).
Palliative radiotherapy	Local radiotherapy for analgesic purposes or for lytic lesions at risk of fracture

Category	Drug Name
	may be carried out if required. Whenever possible, these patients should have a tumor assessment of the lesion(s) before they actually receive the radiotherapy in order to rule out progression of disease. In case of PD, patients should discontinue treatment. No dose modification of study treatment is needed during radiotherapy.
¹ NTI = narrow therapeutic index drugs whose exposure-response indicates that increases in their exposure levels by the concomitant use of potent inhibitors may lead to serious safety concerns (e.g., Torsades de Pointes). ² Herbal product P-gp inducer	

Table 14-8 List of medications to be used with caution¹ during LEE011 treatment

Category	Drug Name
Moderate CYP3A Inhibitors	amprenavir, aprepitant, atazanavir, ciprofloxacin, darunavir/ritonavir, diltiazem, erythromycin, fluconazole, fosamprenavir, grapefruit juice, nilotinib imatinib, tofisopam, cyclosporin, ciprofloxacin, verapamil, dronedarone, crizotinib, casopitant, amprenavir, atazanavir/ritonavir, duranavir, netupitant, schisandra sphenanthera ⁴ , cimetidine, lomitapide
Moderate CYP3A Inducers	bosentan, efavirenz, etravirine, modafinil, nafcillin, genistein, ritonavir, thioridazine, tipranavir, semagacestat, talviraline, lopinavir, lersivirine
Sensitive CYP3A Substrates ²	alpha-dihydroergocryptine, alfentanil, almorexant, aplaviroc, aprepitant, atazanavir, atorvastatin, avanafil, bosutinib, breacanavir, brotizolam, budesonide, buspirone, capravirine, casopitant, conivaptan, danoprevir, darifenacin, darunavir, dasatinib, dronedarone, ebastine, eletriptan, elvitegravir, eplerenone, everolimus, felodipine, fluticasone, ibrutinib, indinavir, ivacaftor, levomethadyl, lomitapide, lopinavir, lovastatin, lumefantrine, lurasidone, maraviroc, midazolam, midostaurin, neratinib, nisoldipine, perospirone, quetiapine, ridaforlimus, saquinavir, sildenafil, simeprevir, simvastatin, ticagrelor, terfenadine, ticagrelor, tilidine,tipranavir, tolvaptan, triazolam, vardenafil, vicriviroc, voclosporin
Known inhibitors of BSEP	atorvastatin, cerivastatin, cyclosporine, glyburide, reserpine, rifampicin, troglitazone, valinomycin,
Sensitive substrates of MATE1 and OCT2	acyclovir, cimetidine, ganciclovir, fexofenadine ¹ , metformin ¹ , procainamide, topotecan, glycopyrronium ¹ , topotecan, 6-beta-hydroxycortisol, amantadine, carboplatin, cisplatin, histamine, lamivudine, linagliptin, metformin, oxyplatin, oxybutynin, phenformin, picoplatin, pramsorafenib, tropisetron, trospium, varenicline, umeclidinium
Sensitive substrates of BCRP	rosuvastatin and sulfasalazine
Medications that carry a possible risk for QT prolongation	alfuzosin, apomorphine, aripiprazole, atazanavir, bedaquiline, bortezomib, bosutinib, clozapine, crizotinib, dabrafenib, dasatinib, dexmedetomidine, dihydroartemisinin+piperazine, dolasetron, eribulin, famotidine, felbamate, fingolimod, foscarnet, fosphenytoin, gatifloxacin, gemifloxacin, granisetron, iloperidone, isradipine, lapatinib, lithium, mifepristone, mirabegron, mirtazapine, moexipril/hctz, nicardipine, nilotinib, norfloxacin, ofloxacin, olanzapine, oxytocin, paliperidone, pasireotide, pazopanib, perflutren lipid microspheres, pipamperone, promethazine, quetiapine, ranolazine, rilpivirine, risperidone, roxithromycin, saquinavir, sertindole, sorafenib, sunitinib, tacrolimus, tamoxifen, telavancin, telithromycin, tetrabenazine, tizanidine, tolterodine, toremifene, vardenafil, vemurafenib, venlafaxine, vorinostat, ziprasidone
¹ Any drug mentioned in the above list should be contraindicated if they are excluded based on any other exclusion criteria as specified in of the Study Protocol or listed in Table 14-1 ² Sensitive substrates: Drugs whose plasma AUC values have been shown to increase 5-fold or higher when coadministered with a potent inhibitor. ³ NTI = narrow therapeutic index drugs whose exposure-response indicates that increases in their exposure levels by the concomitant use of potent inhibitors may lead to serious safety concerns (e.g., Torsades de Pointes).

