7.1.3 Discontinuation of Study Treatment

Patients may voluntarily discontinue from the study or be discontinued from the study at the discretion of the investigator at any time. If a patient decides to discontinue from the study treatment, the investigator must make every effort (e.g. telephone, e-mail, letter) to determine the primary reason for this decision and record this information in the patient's chart and on the appropriate CRF pages. They may be considered withdrawn if they state an intention to withdraw, fail to return for visits, or become lost to follow-up for any other reason.

The investigator should discontinue study treatment for a given patient if he/she believes that continuation would be detrimental to the patient's well-being

If a patient discontinues study treatment, but continues study assessments, the patient remains on study until such time as he/she completes protocol criteria for ending study assessment. At that time, the reason for study completion should be recorded on the Study Phase Completion Disposition CRF page.

End of treatment/premature withdrawal visit is not considered as the end of the study.

Patients who prematurely discontinue study drug should be scheduled for a visit as soon as possible, at which time all of the assessments listed for the EOT visit will be performed ([Table 7-1](#)). This visit should take place no more than 14 days after the last dose of study drug. An EOT eCRF should be completed, giving the date and reason for stopping the study treatment. End of treatment/premature withdrawal visit is not considered as the end of study.

The investigator must contact the IRT to register the patient's discontinuation.

All patients who discontinue study drug should return for assessments according to [Table 7-1](#) including: safety follow-up ([Section 7.1.5.1](#)), disease progression follow-up (if applicable, [Section 7.1.5.2](#)) and survival follow-up ([Section 7.1.5.3](#)).

An End of Phase Disposition eCRF should be completed upon completion of the Disease Progression Follow-Up Period.

Patients may be discontinued from the study drug if any of the following occur:

- Patient withdrew consent
- Adverse event
- Lost to follow-up
- Death
- Non-compliance with study drug

- Physician decision
- Progressive disease
- Protocol deviation
- Study terminated by sponsor
- Technical problems
- Patient/parent/guardian decision

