7.1.5.1 Safety follow-up

All patients must have safety evaluations 30 days after the last dose of study drug, except, in the case of death, loss to follow-up, withdrawal consent, or discontinuation of study treatment to enroll in the LEE011 rollover clinical trial (CLEE011X2X01B). Information related to AEs (including concomitant medication taken for ongoing AEs) and initiation of anti-neoplastic treatments will be collected. All AEs suspected to be related to study drug should

be followed weekly, or as clinically indicated, until resolution or stabilization. Antineoplastic therapies and/or tumor directed surgical procedures initiated during the safety follow-up period must be recorded on the Antineoplastic Therapy since Discontinuation of Study Drug eCRF.

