7.1.5.3 Survival follow-up phase

All patients will be followed for survival via a phone call (or during a clinic visit) every 12 weeks and up to one additional time per quarter if a survival update is required to meet safety or regulatory needs, until any of the following (whichever occurs first): death, withdrawal of consent, loss to follow-up, at least 18 months from when the last patient started treatment, or when 80% of patients have died or been lost to follow-up, or early study termination. Antineoplastic therapies or tumor directed surgical procedures initiated during the survival follow-up period must be recorded on the Antineoplastic Therapy since Discontinuation of Study Drug eCRF.

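### Table 14-7, read literally, takes patients who need other anticancer therapy or surgery off the study, in conflict with the sections that keep them in safety and survival follow-up

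*Protocol*

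**What the plan says.** Protocol Section 14.4.1, Table 14-7, row on other investigational and antineoplastic therapies: chemotherapy, biologic therapy, radiation and surgery are barred for as long as the patient is on the study, and "If such agents are required for a patient then the patient must be discontinued from the study". The table's own title is narrower: "List of prohibited medications during LEE011 treatment".

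The body of the protocol separates stopping treatment from leaving the study.

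- Section 7.1.3: "If a patient discontinues study treatment, but continues study assessments, the patient remains on study", and "End of treatment/premature withdrawal visit is not considered as the end of the study". It also says "All patients who discontinue study drug should return for assessments according to" Table 7-1, naming safety follow-up, progression follow-up where applicable, and survival follow-up.
- Section 7.1.5.1: "All patients must have safety evaluations 30 days after the last dose of study drug". The exceptions are death, loss to follow-up, withdrawal of consent and transfer to the rollover trial.
- Section 7.1.5.3: "All patients will be followed for survival via a phone call (or during a clinic visit) every 12 weeks". The stopping reasons are death, withdrawal of consent, loss to follow-up, reaching the 18-month or 80% limit, and early termination of the study.
- Sections 7.1.5.1 to 7.1.5.3 each require new antineoplastic therapy or surgery to be recorded on a dedicated eCRF, and Table 7-1 schedules that item in all three follow-up columns.

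**The concern.** A site with a patient who needs surgery or another anticancer drug is likely to look in the appendix on prohibited treatment. There it finds a mandatory instruction to take the patient off the study. If it complies, the patient is closed out without the 30-day safety evaluation and without the 12-weekly survival contacts that the main text requires.

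Two things would then be at stake. Deaths and post-treatment safety data would be incomplete, although SAP Section 3.6.2 still lists and summarises all deaths and SAP Section 3.6 still covers safety data up to 30 days after treatment. And if OS and the 12-month OS rate were analysed as in Protocol Section 10.5.2, these patients would be censored at a point that may be related to their prognosis.

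**Working it through.** **Step 1. The passages side by side.** The question is what happens to a patient who needs other anticancer therapy.

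| Place | Answer |
|---|---|
| Table 14-7 | Leaves the study |
| Section 7.1.3 | Stopping drug is not leaving the study; goes on to follow-up |
| Section 7.1.5.1 | 30-day safety evaluation applies; new therapy is not an exception |
| Section 7.1.5.2 | Tumor follow-up ends when new therapy starts |
| Section 7.1.5.3 | Survival follow-up continues; new therapy is not a stopping reason |
| Section 14.1.31 | New therapy completes the post-treatment phase, which comes before survival follow-up |

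Only Table 14-7 ends participation.

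**Step 2. Can the phrase simply mean stopping treatment?** Three places make that reading unsafe. Sections 7.1.5.2 and 7.2.1 explain discontinuation from the study as loss to follow-up or withdrawal of consent, and list new antineoplastic treatment as a separate item. The palliative radiotherapy row of Table 14-7 tells patients with progression to stop treatment, so the same table uses both terms. The glossary says that stopping treatment may or may not coincide with withdrawal of the patient.

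**Step 3. PFS.** Section 7.1.5.2 ends tumor assessments at new therapy, and the Appendix 1 default (Section 14.1.27, situation F) censors PFS at the last adequate assessment. Neither depends on Table 14-7. The planned event number is also untouched: (1.645 + 0.842)² / [(2/9) × (ln 0.33)²] = 22.6, rounded up to the plan's 23.

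**Step 4. OS, illustration only.** The documents give no OS rate, no frequency of new therapy and no prognosis after it, so all inputs here are assumed:

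- S0, 12-month OS under the hazard before new therapy: 50% or 80%.
- f, probability of starting new therapy by 12 months, ignoring death: 10% or 40%.
- r, death hazard after new therapy relative to before: 0.5 to 2.

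With constant hazards, λ0 = -ln(S0)/12, γ = -ln(1-f)/12, λ1 = r·λ0 and a = λ0 + γ - λ1:

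True S(12) = exp[-12(λ0+γ)] + γ·exp(-12λ1)·[1 - exp(-12a)]/a.

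Censoring everyone at new therapy estimates S0 instead.

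Worked case S0 = 0.5, f = 0.4, r = 2: λ0 = 0.0578, γ = 0.0426, λ1 = 0.1155, a = -0.0152. The first term is 0.5 × 0.6 = 0.300. The second is 0.0426 × 0.25 × (1 - 1.2)/(-0.0152) = 0.140. True S(12) = 0.440, against an estimate of 0.500.

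| S0 (the estimate) | f | r | True 12-month OS | Estimate minus truth (points) |
|---|---|---|---|---|
| 50% | 10% | 0.5 | 51.0% | -1.0 |
| 50% | 10% | 2 | 48.6% | +1.4 |
| 50% | 40% | 0.5 | 54.3% | -4.3 |
| 50% | 40% | 2 | 44.0% | +6.0 |
| 80% | 10% | 0.5 | 80.5% | -0.5 |
| 80% | 10% | 2 | 79.2% | +0.8 |
| 80% | 40% | 0.5 | 82.0% | -2.0 |
| 80% | 40% | 2 | 76.4% | +3.6 |

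At r = 1 the difference is zero.

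**The case against.** The best defence is that the cell is loosely worded and the main text governs. The table's title confines it to the treatment period. The introduction to Appendix 4 calls its lists a guide. Section 7.1.3, which is about stopping treatment, itself begins "Patients may voluntarily discontinue from the study or be discontinued from the study at the discretion of the investigator at any time". Section 7.1.4 makes withdrawal of consent the event that ends contact. Loss of follow-up therefore requires a site to let one appendix cell override several body sections. Section 8.2.2 also requires every SAE to be reported until at least 30 days after treatment stops, and suspected related SAEs after that, whether or not a visit takes place.

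Most of this stands, and it is why the point is a risk under the literal reading. It does not remove the conflict: the cell is a mandatory instruction, and the other loose uses add to the ambiguity.

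A reader might infer more, and the documents do not support it.

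- That other therapy would be needed more often on placebo. Patients who progress on placebo may cross over to LEE011 (Section 6.1.4), so the balance between arms is unknown.
- That those removed have the most different prognosis. The need may arise from progression or because a tumor has become resectable, and these plausibly point in opposite directions.
- That the antineoplastic-therapy eCRF pages would be empty. Patients who stop drug for another reason and start therapy later would still fill them.
- That a large OS bias in a known direction follows. A single scenario can be built to show one, but its inputs would all be chosen by the reader.

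**Conclusion.** The contradiction is real and textual. Table 14-7, taken at its word, ends participation for patients whom Sections 7.1.3, 7.1.5.1, 7.1.5.3 and 14.1.31 keep in safety or survival follow-up. That any patient was actually lost this way is not shown.

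The present effect is small. Ten patients were enrolled before recruitment was halted (Amendment 3), SAP Section 4 drops the PFS and OS analyses, and Protocol Section 2.2 already accepts that crossover weakens the OS estimate. What remains live is the completeness of death reporting and post-treatment safety data.

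For OS as planned in Section 10.5.2, the possible error in the 12-month rate runs from about -4 to +6 percentage points over the assumed grid. That rests on constant hazards and on starting new therapy being unrelated to risk beforehand. Other assumptions would give other values, and neither size nor sign can be read from the documents. PFS is not affected.

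**What to change.** Reconcile the Table 14-7 cell with Sections 7.1.3 and 7.1.5.1 to 7.1.5.3. It should state that needing such therapy does not in itself end study participation, and that the patient stays in safety follow-up (7.1.5.1) and survival follow-up (7.1.5.3), with the therapy recorded on the existing eCRF for antineoplastic therapy since discontinuation. Tumor assessments continue to follow Section 7.1.5.2.

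Leave the treatment prohibition itself unchanged. Its scope is stated in two ways, the whole time on study in the cell and LEE011 treatment in the title, and the sponsor should reconcile these.

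The cost is one table cell, carried in a written amendment with the approvals that Section 12.1 requires. No visit, eCRF page or analysis has to be added.

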6.3.3 Prohibited concomitant therapy

The following medications are prohibited during treatment in this study ([Appendix 4](#)):

- Strong inhibitors or inducers of CYP3A4/5
- Substrates of CYP3A4/5 with narrow therapeutic index

- Medications with a known risk for QT prolongation
- Other investigational and antineoplastic therapies
- Herbal medications
- Primary prophylactic hematopoietic growth factors
- Palliative radiotherapy
- Patients must avoid consumption of grapefruit, grapefruit hybrids, pummelos, star-fruit, Seville oranges or products containing the juice of each during the entire study and preferably for an additional 7 days before the first dose of study medications, due to potential CYP3A interaction with the study medications. Orange juice is allowed.

Refer to the LEE011 Investigator's Brochure and [Appendix 4](#) for information on possible interactions with other drugs.

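### Palliative radiotherapy is banned outright in Protocol Section 6.3.3 but allowed for stated purposes in Appendix 4, Table 14-7, so its status as a protocol deviation is unclear

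*Protocol*

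**What the plan says.** Three places in the protocol bear on radiotherapy during treatment.

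- **Section 6.3.3.** The list opens with "The following medications are prohibited during treatment in this study" and points to Appendix 4. One bullet reads, in full, "Palliative radiotherapy". It is separate from the bullet on other investigational and antineoplastic treatment.
- **Section 14.4.1, Table 14-7, palliative radiotherapy row.** The table is titled "List of prohibited medications during LEE011 treatment". This row nevertheless says that local radiotherapy for analgesia, or for lytic lesions that might fracture, "may be carried out if required". It asks for a tumor assessment beforehand where possible, to exclude progression, and for treatment to stop if progression is found. It adds "No dose modification of study treatment is needed during radiotherapy".
- **Section 14.4.1, Table 14-7, row on other anticancer treatment.** "Other investigational anticancer therapies including chemotherapy, biologic or radiation therapy, and surgery must not be used while the patient is on the study". The consequence follows: "If such agents are required for a patient then the patient must be discontinued from the study".

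On the reporting side, SAP Section 3.2.2 drops the protocol deviation analyses and refers to SAP Section 4. Section 4 keeps a listing of patients with deviations and omits the summary tables. Section 4 also states that PFS and the response endpoints will not be analyzed.

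**The concern.** A site that reads only Section 6.3.3 would conclude that palliative radiotherapy is barred while the patient is on study drug. A site that follows the cross-reference to Table 14-7 would find the same treatment allowed for two purposes, with dosing continuing. Both sites would believe that they were following the protocol.

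Two things are at stake. The first is consistent conduct: treatment has no fixed duration, and Amendment 3 reports patients still being treated. The second is the deviation listing. The same act is a deviation under Section 6.3.3 and permitted under the palliative row of Table 14-7, so the listing could depend on which page the person coding it consulted.

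**Working it through.** The plan gives no figure to reproduce on this point, so the check is a comparison of texts.

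**Step 1. Section 6.3.3 against the palliative row.** The treatment is named identically in both places. One place prohibits it without condition; the other permits it for pain or fracture risk and leaves the dose unchanged. No wording in Section 6.3.3 limits its bullet to other uses. The two cannot both be followed for a patient irradiated for pain.

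**Step 2. Is the bullet merely shorthand for the table row?** Hematopoietic growth factors are a useful comparison. Their row in Table 14-7 also mixes a ban with a permitted use. There, however, the Section 6.3.3 bullet is limited to primary prophylaxis, and Section 6.3.1 lists therapeutic use and secondary prophylaxis as permitted. For radiotherapy, the Section 6.3.3 bullet carries no limit and Section 6.3.1 does not mention it. The protocol qualified one partial ban in its body text and not the other.

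**Step 3. The row on other anticancer treatment.** Its subject is investigational anticancer therapy. It names radiation within that, and it requires discontinuation from the study. It neither includes nor excepts local palliative irradiation. Because palliative radiotherapy has its own row, the two rows can be read as a general rule with a specific exception, but the exception is not written down.

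**Step 4. Consequence for the deviation listing.**

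| Text read | Local radiotherapy for pain, study drug continued |
|---|---|
| Section 6.3.3 | Prohibited therapy, so a deviation |
| Table 14-7, palliative row | Permitted, so not a deviation |
| Table 14-7, row on other anticancer treatment | Depends on whether palliative use is excepted |

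**Step 5. Reach into the efficacy analysis.** Protocol Section 10.4.3 does not mention radiotherapy or new anticancer therapy. Appendix 1 supplies a default: in Table 14-5, situation F, a patient given new anticancer therapy is censored at the last adequate assessment, and Section 14.1.39 lists that as a censoring reason. No text says whether palliative radiotherapy falls under this default. The gap changes no planned output, since SAP Section 4 drops the log-rank test, hazard ratio, Kaplan-Meier estimates and response summaries, and SAP Section 3.4.3 drops the supportive analyses.

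**Step 6. Scale.** The inputs are 10 patients enrolled and 4 on treatment on 18-Aug-2017 (Amendment 3 study status). The documents give no frequency of palliative radiotherapy, so the number of patients affected lies anywhere from 0 to 10 over the study, and from 0 to 4 among those still on treatment at that date.

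**The case against.** The best defense is that Section 6.3.3 sends the reader to Appendix 4, where the detailed instruction sits, so the bullet is a pointer and the table governs. The row on other anticancer treatment concerns treatment of the cancer, and a specific palliative row would override a general one. The part about the two table rows largely stands. A reader might infer that three statements contradict one another outright, and the documents do not support that: the general row is unclear on palliative use but can be read consistently with the palliative row. The defense does not rescue Section 6.3.3, which names the treatment, prohibits it and states no exception.

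A reader might also infer that the protocol has no rule for progression in an irradiated patient. That goes too far. The palliative row has its own progression check before irradiation, and Appendix 1 has the default for new anticancer therapy. What is missing is narrower: whether palliative radiotherapy counts as such therapy. Appendix 1 (Section 14.1.27) asks the protocol to specify situation F in detail and Section 10.4.3 does not, but that is missing detail for an analysis that will not be run.

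A third tempting inference is bias in PFS, because an irradiated lesion might shrink and delay progression. The documents give no data on this. Under Section 14.1.4 a lytic lesion is measurable only through a soft tissue component of sufficient size, so many such lesions might not enter the sum of diameters at all. Expressing one patient as 1/23 = 4.3% of planned events or 1/10 = 10% of those enrolled does not measure an effect either. Ten patients contribute at most 10 first PFS events, so the 23 will not be reached.

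Finally, deviation classes may be set in documents not seen here: Section 10.1.3 refers to the RAP for major deviations, and the SAP refers to a separate module for severity codes. A class set there could settle the listing but would not tell sites which instruction to follow.

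**Conclusion.** The protocol contradicts itself on palliative radiotherapy: Section 6.3.3 prohibits it without qualification, and the palliative row of Table 14-7 permits it for two purposes. The row on other anticancer treatment leaves open whether palliative use is excepted. Sites could handle the same patient in opposite ways, and the deviation status would follow whichever text was read.

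The practical weight is modest. It falls on conduct for the few patients still treated and on the entries in one retained listing. Its size cannot be computed without a radiotherapy frequency. There is no effect on PFS, response or per-protocol results in the current report, because none of these will be produced. This conclusion rests on the SAP's short close-out scope remaining in force and on the current text of Sections 6.3.3 and 14.4.1 being what sites use. The documents do not settle which clinical rule is right, and no view on that is taken here.

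**What to change.** Reconcile Section 6.3.3 with both rows of Table 14-7 so that they give one instruction, stating explicitly whether the row on other anticancer treatment covers palliative radiotherapy. The sponsor decides the clinical rule. Then state, to match that rule, whether on-study palliative radiotherapy is a protocol deviation for the listing kept under SAP Section 4, and apply this to any case already recorded.

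No change to Section 10.4.3 is needed for the current report. If a PFS analysis were ever reinstated, one sentence should say whether palliative radiotherapy falls under situation F of Table 14-5 and how an irradiated lesion is assessed afterwards.

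The cost is protocol wording, with the approvals that an amendment requires under Section 12.1, and a check of existing deviation entries. No new data, patients or analyses are required.
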